## **5.- Recruitment**

All patients who meet the inclusion and exclusion criteria will be offered preoperative participation in this study. Once the information has been understood (Annex 1) and the written informed consent (Annex 2) has been signed, each patient will be assigned a code that will be used to anonymously manage any of their information obtained during the study. Thus, the confidentiality of the data belonging to all the patients included in the study will be guaranteed at all times from the moment of recruitment.

## **6.- Intervention**

The patient will undergo the indicated surgical intervention depending on whether it is an esophageal or gastric neoplasm, with curative intent with or without prior neoadjuvant treatment. Surgical intervention and postoperative care will be carried out in each of the centers of the national territory that commit to participate according to their usual clinical practice. Thus, the perioperative management and care protocol will be that of each center without the need to apply exceptional measures (beyond the control of the clinical and analytical variables of this study) or a homogeneous protocol in all the participating centers.

The analysis and control of the preoperative clinical variables must be carried out the day before or the same day of the surgical intervention prior to it.

## **7.- Follow up**

The patient will be monitored during the first 90 postoperative days, compiling all the specific variables of this study and the possible complications and mortality that occurred in this period.

During the immediate postoperative period, apart from the care applied routinely in each center, patients should be evaluated daily and the clinical and laboratory variables specified later should be collected on days 1, 2, 3, 4 and 6 postoperatively. In the same way, in this postoperative course, the possible complications that appeared during the hospital stay will be compiled.

Subsequently, if the patient is discharged from the hospital, a follow-up will be carried out in the outpatient consultations at 30 and 90 days to evaluate the possible complications that appear in this period and other variables studied will be completed.

## **8.- Database and study variables**

The variables collected throughout the study protocol will be collected on the following dates of assistance, care, control and follow-up of the patient.

### **8.1.- FORMAT and ACCESS to the DATABASE**

A database included in the REDCAP of the AEC has been designed to collect the different variables included in this study.

For access to said database, the passwords will be provided to each participating center.

## **8.2.- PARTS of the DATABASE**

After opening the REDCAP application of the AEC, you can access the data set and the different variables to be collected at each moment of the care process and which will be described in more detail below:

The main outcome variable of the study is ANASTOMOTIC LEAKAGE, a categorical variable divided into the following categories, according to the consensus definitions of the Consensus Group on Complications of Esophagectomy (ECCG) (27), which in this study will be applicable both to fistulas occurred after esophagectomy and after gastrectomy:

- NO: If this complication did not occur.
- I: Defect that does not require specific treatment or that can be treated medically or with diet modification
- II: Defect that requires some intervention, but not surgical, such as: drainage by interventional radiology, prosthesis placement, opening of the wound at the bedside, compression or wound healing.
- III: Defect requiring surgical intervention

In relation to this variable, the following data are also included in the study:

- DAY Dx LEAK (DAY of DIAGNOSIS OF THE ANASTOMOTIC LEAK: ordinal variable that shows the number of the postoperative day on which the diagnosis of the anastomotic leak occurred.
- EDA Dx LEAK (LEAK DIAGNOSIS THROUGH ENDOSCOPY): Dichotomous variable: YES/NO.
- CAT Dx LEAK (DIAGNOSIS OF LEAK BY CAT): Dichotomous variable: YES/NO.

The rest of the variables collected in this study are:

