## OBJECTIVES

Based on the hypothesis of the study, the main and secondary objectives of this study are established:

- Main goal:

\*Design a predictive model based on clinical and analytical variables that allow identifying patients with a high risk of anastomotic leak (main variable) during the postoperative period of esophagogastric surgery.

- Secondary objectives:

\* Design a predictive model based on clinical and analytical variables that allow identifying patients at high risk of other major complications (Clavien-Dindo greater than 3) during the postoperative period of esophagogastric surgery.

\* Individually describe the postoperative evolution of the clinical and analytical parameters studied in patients without major complications or AF and those who did suffer from any of them.

\* Describe the complications and types of AF diagnosed in the study.

\* Assess the day AF was diagnosed and the treatment used for its possible resolution.

\* Assess the day AF was diagnosed and hospital stay.

\* Compare the preoperative Glasgow prognostic score (mGPS) and the biochemical value of inflammatory markers (CRP, Interleukin 6 (IL-6) and procalcitonin) and the appearance of AF.

\* Assess the AF resolution capacity of each technique used.

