### 1.- Type of design

Prospective and multicenter study that aims to develop, with the help of artificial intelligence methods, a tool and predictive model that allows identifying cases with a high risk of anastomotic leak and/or major complications through the analysis of different clinical and analytical variables collected during the postoperative period. of patients undergoing esophagectomy or gastrectomy.

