### Category M

M0 No distant metastasis

M1 Distant metastasis

- ECOG (ECOG functional classification): Categorical variable divided into the following categories:

- 0: Asymptomatic. Fully active.

- 1: Restriction of intense activity. Capable of ordinary work.

- 2: Ambulatory and capable of self-care. Inability to work. Up more than 50% of the time awake.

- 3: Capable of some self-care. Life bed-chair more than 50% of the time awake.

- 4: Total disability. Chair-bed 100% of the time awake

- 5: Dead

- ASA (ASA Classification): Categorical variable divided into: 1, 2, 3 and 4.

- DM (Diabetes Mellitus): Dichotomous variable: YES/NO.

- AHT (Arterial hypertension): Dichotomous variable: YES/NO.

- HEART DISEASE: Heart failure or ischemic heart disease. Dichotomous variable: YES/NO.

- NEPHROPATHY: Chronic renal failure. Dichotomous variable: YES/NO.

- SMOKER: Dichotomous variable: YES/NO.

- PNEUMOPATHY: Chronic obstructive pulmonary disease or Emphysema. Dichotomous variable: YES/NO.

- CEREBRAL VASC DISEASE (Cerebral Vascular Disease): Dichotomous variable: YES/NO.

- ENF ARTER PERIF (Peripheral arterial disease): Dichotomous variable: YES/NO.

- DEMENTIA: Dichotomous variable: YES/NO.

- STEROIDS: Taking corticoid medication. Dichotomous variable: YES/NO.

- OTHER AP (PERSONAL BACKGROUND): write the most relevant

- CONDITIONING (CONDITIONING OF GASTRIC PLASTY): Dichotomous variable: YES/NO.
- DATE CIR (DATE OF INTERVENTION): in day/month/year format
- TYPE OF SURGERY: Categorical variable divided into the following categories:
  - IVOR LEWIS ESOPHAGECTOMY: 2-stage esophagectomy
  - MCKEOWN ESOPHAGECTOMY: 3-stage esophagectomy
  - TRANSHIATAL ESOPHAGECTOMY: 2-stage transhiatal esophagectomy
  - TOTAL ESOPHAGOGASTRECTOMY: Total esophagogastrectomy
  - SUBTOTAL GASTRECTOMY: Subtotal gastrectomy
  - TOTAL GASTRECTOMY: Total gastrectomy
  - POLAR SUPERIOR GASTRECTOMY: Polar superior gastrectomy
  - EXTENDED TOTAL GASTRECTOMY: Extended total gastrectomy
  - OTHERS: Others
- APPROACH (SURGICAL APPROACH): Categorical variable divided into the following categories:
  - TOTAL ROBOT Total Robotic Approach
  - HYBRID Combined approach to abdomen and thorax: open + robot, open + MIS, MIS + robot
  - MIS TOTAL Laparoscopy and thoracoscopy approach (+/- cervicotomy)
  - FULL OPEN Full open approach
- BLOOD LOSS (ESTIMATED INTRAOPERATIVE BLOOD LOSS): Continuous variable expressed in ml.

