### 2.- Data análisis

The statistical study will be carried out with the help of the SPSS® version 23.0 software for Windows, using the MATLAB® programming environment for the preparation of the predictive model based on artificial neural networks (ANN).

In the first place, a descriptive analysis will be carried out, both of the sociodemographic and clinical variables, as well as of the analytics and the results of the study.

To describe the quantitative variables that follow a normal distribution, the mean and standard deviation will be used, and the median and interquartile range for those that do not follow a normal distribution, as well as histograms with normality curves for their graphical description.

For the qualitative variables, frequencies and percentages will be used, using bar graphs and/or sectors for the graphic description of those with greater relevance.

A univariate study will be performed to relate the variables studied with the appearance of AF and major postoperative complications. For this, different tests will be used depending on the variable to be studied:

- a) Normal categorical variables: Chi-square test or Fisher's exact test.
- b) Normal continuous variables: Student's t-test.
- c) Non-normal continuous variables: Mann-Whitney U test.

In the results obtained from the univariate study, those variables that show a  $p < 0.1$  after the application of the corresponding tests will be considered as related or candidates to predict AF or major

complications. This value will be considered more conservative, different from the conventionally accepted value of 0.05, with the intention of not ruling out potential variables that could have some influence on the results of the study.

Once the univariate study has been completed, a multivariate study will be carried out, using the logistic regression (RL) method. To do this, a recoding of the variables will be carried out, transforming the categorical variables into dummy variables. It will be verified that the variance inflation factor (VIF) is less than 2 in all cases, thus ruling out important problems of collinearity between the variables.

On the other hand, a predictive model based on artificial neural networks (ANN) will also be developed, using a Multilayer Perceptron, a multilayer neural network of forward connections, without recurrent connections and supervised learning.

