4.- Another possible limitation of the study could be the differences in the surgical technique and the specific perioperative management protocols of each center, which, being different and particular in each one of them, would facilitate a wide variability in the management of the cases. However, the purpose of the study is to create a predictive model that is universal and based on objective clinical and analytical variables, in order to obviate these differences between centers and with the ability to be applied in each of them with the same effectiveness.

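### One leak model covers esophagectomy and gastrectomy, with no performance by operation, so part of its pooled discrimination may only reflect which operation was done

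*Combined protocol and SAP*

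**What the plan says.** The main objective (Objectives) is one model for "identifying patients with a high risk of anastomotic leak (main variable) during the postoperative period of esophagogastric surgery". Type of design (section 1 of Material and methods) describes the data as "collected during the postoperative period. of patients undergoing esophagectomy or gastrectomy". Section 8.2 takes the leak grading from an esophagectomy consensus group, "which in this study will be applicable both to fistulas occurred after esophagectomy and after gastrectomy".

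Section 8.2.1 records the operation ("TYPE OF SURGERY: Categorical variable divided into the following categories"), in nine categories that run from subtotal gastrectomy to three-stage esophagectomy. It also records the anastomosis and the tumour location. Section 8.2.2 lists the clinical and laboratory values collected before surgery and on days 1, 2, 3, 4 and 6.

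Under Data analysis (section 2 of Data collection and analysis), "A univariate study will be performed to relate the variables studied with the appearance of AF and major postoperative complications". Variables with p<0.1 become candidates, a logistic regression with dummy-coded categorical variables follows, and "a predictive model based on artificial neural networks (ANN) will also be developed, using a Multilayer Perceptron". The section names no performance measure. Nowhere does the protocol mention separate models, stratification, a marker-by-operation term, performance by operation, or a reference model based on the operation alone.

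Limitations, item 4, states the purpose as to "create a predictive model that is universal and based on objective clinical and analytical variables". The protocol then plans a mobile or web application giving predictions for individual new patients.

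**The concern.** The hypothesis is that daily postoperative clinical and laboratory values can reveal a leak early. The operation is known before the first postoperative blood sample. If leak risk differs between operations, any predictor that carries information about the operation will separate leak from non-leak patients in the pooled cohort. This applies to the operation itself, to the anastomosis or location, and to a marker that simply runs higher after the larger procedure. A pooled performance figure then mixes two things: differences in risk between operations, and detection of a leak among patients who had the same operation. Only the second is new information at the bedside.

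As written, the plan yields no result that separates them. The tool could be released for all esophagogastric resections without evidence on how well the markers work within either operation. The biomarker studies in the Introduction that concern leak after upper gastrointestinal surgery come mainly from esophageal resection, so similar marker behaviour after gastrectomy cannot be taken for granted.

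**Working it through.** **Figure to reproduce.** The plan states no AUC or other performance figure, so there is none to reproduce. AUC is used here as the usual measure of discrimination.

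**Inputs from the documents.** The Introduction gives leak after esophagectomy as 0-34% and quotes one retrospective series at 16%. It gives no leak rate for gastrectomy, and no section gives the expected case mix. Section 4 (Sample size) gives 847 patients.

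**Assumptions.** Leak rate 16-20% after esophagectomy (pE) and 5-10% after gastrectomy (pG); share of esophagectomies f = 30-50%.

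**Step 1: operation label alone.** Let P = f·pE + (1-f)·pG be the overall leak rate. The share of esophagectomies is a = f·pE/P among leaks and b = f·(1-pE)/(1-P) among non-leaks. A predictor that knows only the operation has AUC = 0.5 + (a-b)/2.

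| pE v pG | f | P | a | b | AUC |
|---|---|---|---|---|---|
| 16% v 10% | 30% | 0.118 | 0.407 | 0.286 | 0.56 |
| 20% v 10% | 40% | 0.140 | 0.571 | 0.372 | 0.60 |
| 16% v 5% | 40% | 0.094 | 0.681 | 0.371 | 0.66 |
| 20% v 5% | 40% | 0.110 | 0.727 | 0.360 | 0.68 |
| equal rates | any | | a = b | | 0.50 |

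Over the assumed range the AUC runs from 0.56 to 0.68.

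**Step 2: a marker with no leak signal.** Suppose a normally distributed marker is δ SD higher after esophagectomy but has the same distribution with and without leak within each operation. Its AUC within each operation is 0.50. Its pooled AUC is 0.5 + (a-b)·[Φ(δ/√2) - 0.5]. With 16% v 5% and f = 40%, a-b = 0.310:

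- δ = 0.5: 0.5 + 0.310 × 0.138 = 0.54
- δ = 1.0: 0.5 + 0.310 × 0.260 = 0.58
- δ = 1.5: 0.5 + 0.310 × 0.356 = 0.61

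Such a marker could pass an unadjusted univariate screen. Leaving the operation out of the predictors would therefore not remove the problem.

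**Step 3: a weak marker combined with the operation.** Simulations of 1,000,000 patients (f = 40%) combined the operation with a marker of fixed within-operation AUC.

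| Within-operation AUC | Pooled, 15% v 5% | Pooled, 20% v 5% |
|---|---|---|
| 0.60 | 0.69 | 0.73 |
| 0.70 | 0.75 | 0.78 |

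**Step 4: an indication from the documents.** The Introduction gives overall morbidity of about 60% after esophagectomy and complications of 40-50% for gastric cancer. At f = 40%, the Step 1 formula gives an operation-only AUC of 0.55 (60% v 50%) to 0.60 (60% v 40%). This concerns any complication, not leak.

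**Step 5: precision by operation.** With 847 patients, f = 40% and 5% gastrectomy leak, 847 × 0.6 × 0.05 gives about 25 leaks among 508 gastrectomies. The Hanley-McNeil variance for AUC 0.70 uses Q1 = 0.70/1.30 = 0.538 and Q2 = 2 × 0.49/1.70 = 0.576. It is [0.21 + 24 × 0.0485 + 482 × 0.0865]/(25 × 483) = 0.00357. The SE is 0.060 and the 95% interval about ±0.12.

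**The case against.** **Pooling is deliberate and legitimate.** The target population is esophagogastric surgery, and the operation is a proper predictor of absolute risk. This stands. A reader might infer that pooling is itself the error; the documents do not support that, and the pooled model should be kept.

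**The modelling may already handle part of this.** If the operation is retained in the logistic regression, marker coefficients are adjusted for it, which weakens the scenario in Step 2. A multilayer perceptron can also represent marker-by-operation interaction without a pre-specified term. Both points are fair. However, nothing guarantees that the operation is retained, and neither point produces a performance result by operation. With the operation in the model, its contribution still enters the pooled AUC.

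**The size is assumed.** This also stands. The documents give neither the gastrectomy leak rate nor the case mix, and with equal leak rates the effect on AUC is nil.

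**A tempting stronger reading** is that the model would recognise the operation instead of detecting leaks, or that a good pooled AUC could hide a complete lack of discrimination. The figures do not support it. Under the main assumptions the label alone reaches at most 0.68 and the null marker 0.61, and neither is a good AUC. The pooled values of 0.75-0.78 in Step 3 arise with a marker that truly discriminates within operation (0.70). The right word is partly.

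**The wording cited is indirect.** The sentence in section 8.2 shows only a shared outcome definition; the pooling follows from Objectives, Type of design and Data analysis. In Limitations, item 4, universality is discussed as applicability across centers with different techniques and protocols, not across operations. The plan therefore does not assert equal performance after both operations; it leaves the question unaddressed.

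**The wider gap** is that Data analysis names no performance measure at all. True, but adding only a pooled measure would leave this point open.

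**Conclusion.** The concern holds in a limited form. As written, the plan cannot show that the markers detect leak among patients who had the same operation, although the tool is meant for all of them. If leak risk differs by operation, some of the pooled discrimination will be information that the clinician already has: an operation-only AUC of 0.56-0.68 under the assumed leak rates and case mix, and 0.54-0.61 for a null marker shifted by 0.5-1.5 SD (16% v 5%, 40% esophagectomies). If the rates are equal, both fall to 0.50. The existence of the gap rests on the text alone; its size rests on leak rates and a case mix that the protocol does not give. It is worth correcting before analysis, because it decides what can be concluded about each operation, but it does not invalidate the design.

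**What to change.** Keep the pooled model and its overall performance. In Data analysis, pre-specify alongside them:

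- discrimination and calibration, with confidence intervals, separately for esophagectomy and for gastrectomy;
- the gain in performance over a reference model containing only procedure and anastomosis.

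Treat marker-by-procedure interactions as exploratory. Limit the claim of a universal tool to operations in which within-operation performance has been shown, and say so in the application.

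The data are already collected under sections 8.2.1 and 8.2.2, so the cost is a few additional analyses. The drawback is precision: about ±0.12 around a gastrectomy AUC of 0.70 under the assumptions in Step 5, and wider if recruitment falls short of 847, which section 4 allows. For that reason the results by operation should accompany the overall result and not replace it.

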## **GASTRIC CANCER**

### Category T

Tx Primary tumor cannot be assessed

T0 No evidence of primary tumor

Tis Tumor in situ

T1 Tumor invades mucosa or submucosa

T1a Tumor invades mucosa

T1b Tumor invades submucosa

T2 Tumor invades the muscularis propria

T3 Tumor invades the subserosa

T4 Tumor invades serosa or neighboring structures

T4a Tumor invades serosa

T4b Tumor invades neighboring structures

### Category N

N- No regional lymph node metastasis

N+ Metastasis in 7 or more regional lymph nodes

### Category M

M0 No distant metastasis

M1 Distant metastasis

- ECOG (ECOG functional classification): Categorical variable divided into the following categories:

- 0: Asymptomatic. Fully active.

- 1: Restriction of intense activity. Capable of ordinary work.

- 2: Ambulatory and capable of self-care. Inability to work. Up more than 50% of the time awake.

- 3: Capable of some self-care. Life bed-chair more than 50% of the time awake.

- 4: Total disability. Chair-bed 100% of the time awake

- 5: Dead

- ASA (ASA Classification): Categorical variable divided into: 1, 2, 3 and 4.

- DM (Diabetes Mellitus): Dichotomous variable: YES/NO.

- AHT (Arterial hypertension): Dichotomous variable: YES/NO.

- HEART DISEASE: Heart failure or ischemic heart disease. Dichotomous variable: YES/NO.

- NEPHROPATHY: Chronic renal failure. Dichotomous variable: YES/NO.

- SMOKER: Dichotomous variable: YES/NO.

- PNEUMOPATHY: Chronic obstructive pulmonary disease or Emphysema. Dichotomous variable: YES/NO.

- CEREBRAL VASC DISEASE (Cerebral Vascular Disease): Dichotomous variable: YES/NO.

- ENF ARTER PERIF (Peripheral arterial disease): Dichotomous variable: YES/NO.

- DEMENTIA: Dichotomous variable: YES/NO.

- STEROIDS: Taking corticoid medication. Dichotomous variable: YES/NO.

- OTHER AP (PERSONAL BACKGROUND): write the most relevant

- CONDITIONING (CONDITIONING OF GASTRIC PLASTY): Dichotomous variable: YES/NO.
- DATE CIR (DATE OF INTERVENTION): in day/month/year format
- TYPE OF SURGERY: Categorical variable divided into the following categories:
  - IVOR LEWIS ESOPHAGECTOMY: 2-stage esophagectomy
  - MCKEOWN ESOPHAGECTOMY: 3-stage esophagectomy
  - TRANSHIATAL ESOPHAGECTOMY: 2-stage transhiatal esophagectomy
  - TOTAL ESOPHAGOGASTRECTOMY: Total esophagogastrectomy
  - SUBTOTAL GASTRECTOMY: Subtotal gastrectomy
  - TOTAL GASTRECTOMY: Total gastrectomy
  - POLAR SUPERIOR GASTRECTOMY: Polar superior gastrectomy
  - EXTENDED TOTAL GASTRECTOMY: Extended total gastrectomy
  - OTHERS: Others
- APPROACH (SURGICAL APPROACH): Categorical variable divided into the following categories:
  - TOTAL ROBOT Total Robotic Approach
  - HYBRID Combined approach to abdomen and thorax: open + robot, open + MIS, MIS + robot
  - MIS TOTAL Laparoscopy and thoracoscopy approach (+/- cervicotomy)
  - FULL OPEN Full open approach
- BLOOD LOSS (ESTIMATED INTRAOPERATIVE BLOOD LOSS): Continuous variable expressed in ml.
- PLASTY TYPE: Categorical variable divided into the following categories: STOMACH, COLON, JEJUNUM and OTHERS.
- VIA ASCENT (FROM THE PLASTIA TO MAKE THE ANASTOMOSIS): Categorical variable divided into the following categories: MEDIASTINO, RETROESTERNAL and SUBCUTANEOUS.
- ANASTOMOSIS: Categorical variable divided into the following categories:
  - CERVICAL ESOPHAGUS-PLASTY
  - INTRATHORACIC ESOPHAGUS-PLASTY
  - GASTROJEJUNOSTOMY
  - ESOPHAGOGJEJUNOSTOMY
- ANASTOMOSIS TYPE: Categorical variable divided into the following categories:
  - MANUAL Manual
  - CIRCULAR MECHANICS Circular mechanics with CEEA (includes Orvil)
  - MECHANICAL L-L Lateral-lateral mechanics
  - OTHER Other
- PYLORUS (ACT ON THE PYLORUS): includes the performance of pyloromyotomy, pyloroplasty, endoscopic dilation of the pylorus, injection of botulinum toxin, or any other procedure on the pylorus to facilitate emptying of the plasty. Dichotomous variable: YES/NO.
- ICG (USE OF INTRAOPERATIVE FLUORESCENCE TO EVALUATE THE VASCULARIZATION OF THE PLASTY AND OF THE AREA OF THE ANASTOMOSIS): Dichotomous variable: YES/NO.
- pTNM TUMOR STAGING (includes the variables pT, pN and pM): based on the pathological study of the piece resected in the intervention.

Esophageal and GEJ cancer.

Category T

Tx Primary tumor cannot be assessed

T0 No evidence of primary tumor

Tis High-grade dysplasia defined as the presence of malignant cells confined to the epithelium by the basement membrane

T1 Tumor invades lamina propria, muscularis mucosae, or submucosa

T1a Tumor invades the lamina propria or muscularis mucosae

T1b Tumor invades submucosa

T2 Tumor invades the muscularis propria

T3 Tumor invades adventitia

T4 Tumor invades neighboring structures

T4a Tumor invades pleura, pericardium, azygos vein, diaphragm, or peritoneum

T4b Tumor invades other structures such as aorta, vertebrae, or airway

Category N

Nx Regional lymph nodes cannot be assessed

N0 No regional lymph node metastasis

N1 Metastasis in 1-2 regional lymph nodes

N2 Metastasis in 3-6 regional lymph nodes

N3 Metastasis in 7 or more regional lymph nodes

Category M

M0 No distant metastasis

M1 Distant metastasis

Gastric cancer.

Category T

Tx Primary tumor cannot be assessed

T0 No evidence of primary tumor

Tis Tumor in situ

T1 Tumor invades mucosa or submucosa

T1a Tumor invades the mucosa

T1b Tumor invades submucosa

T2 Tumor invades the muscularis propria

T3 Tumor invades subserosa

T4 Tumor invades serosa or neighboring structures

T4a Tumor invades serosa

T4b Tumor invades neighboring structures

Category N

N- No regional lymph node metastasis

N1 Metastasis in 1-2 regional lymph nodes

N2 Metastasis in 3-6 regional lymph nodes

N3 Metastasis in 7 or more regional lymph nodes

Category M

M0 No distant metastasis

M1 Distant metastasis

